Community health workers in twelve clinics will identify at least 588 symptomatic contacts (*i.e.* possible TB patients) among 1764 household and close contacts in approximately 2304 eligible index patient clusters over a 16-month period, or up to 7 contacts needing evaluation for TB per referring clinic during each two-month block. With this sample size, assuming a clinic intra-cluster correlation coefficient (ICC) of 0.043 and within-index- patient-cluster ICC of 0.7, and accounting for covariates, we will have 83% power to detect a 15% or greater increase in the proportion completing evaluation from 20% to 35%, at alpha of 0.05, following crossover to the intervention. These estimates account for the proposed stepped-wedge design with 6 steps and a one-step transition period (*i.e.*, an “incomplete” design) at each site. Sample size estimates were reached using PASS 15 and Stata 14, with an extension to account for multiple levels of clustering as per Hemming et al. because index patients and contacts are participants in routine services, and the design of a stepped wedge trial has a fixed duration, we will not limit enrollment if it exceeds these numbers, which may be up to four-fold higher in some or all sites, or more if the intervention strategy is highly effective. For example, if up to 1932 symptomatic contacts, or 23 contacts needing evaluation for TB per referring clinic are identified during each two-month block, we would have 91% power to detect a 10% or greater proportion increase in the proportion completing evaluation from 20% to 30%, at alpha of 0.05, assuming the above noted ICCs.

Evaluation of the fidelity of the intervention strategy

We will propose parallel convergent mixed-methods studies involving quantitative assessments of the fidelity of the implementation strategy and its behavioral mechanisms, using validated psychosocial scales, and we will assess other aspects of fidelity, adaptation, and context through qualitative studies involving interviews and focus group discussions with cases, contacts, community health workers, and community health riders.

However, prior to that, we describe our plans in this protocol to validate quantitative study instruments.

Quantitative studies

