To inform our sample size calculations, we used a conservative estimate of the average number of index TB patients of 11 per clinic per 8-week block period (g), assuming a rho-alpha of 0.172 and rho-beta of 0.647 from our preliminary data, and an average number of symptomatic contacts per index TB case (m) of 1, as well as a pre-intervention proportion of patients completing treatment (p1) of 0.4, a post-intervention proportion of treatment completion (p2) of 0.6, the number of clusters crossing at each step (k) of 2, and total steps (steps) of 6.

Using the Stata command:

steppedwedgeTwoLevelsD, binomial complete(1) vartotal(1) p1(0.4) p2(0.6) m(1) k(2) rho(0.172) rho2(0.647) alpha(0.05) steps(6) g(11),

We estimate that the trial will conservatively need 924 total symptomatic contacts of index TB patients to achieve a power of 99%. Sample size estimates were reached using PASS 15 and Stata 16, with an extension to account for multiple levels of clustering as per Hemming et al.[3] and Davis-Plourde [4]. Although some sample size estimators predict 100% power, 100% power is not theoretically achievable, and therefore rendered as 99%. Because index patients and contacts are participants in routine services, we will not limit enrollment if it exceeds these numbers, which we project may be higher by four-fold or greater if the intervention strategy is highly effective.

Tests for Two Proportions in a Stepped-Wedge Cluster-Randomized Design

Design type: Complete

Test statistic: Wald Z-Test

$H_0: P_1 - P_2 = 0$.

$H_A: P_1 - P_2 = D_1 \neq 0$.

ICC (intra-cluster correlation coefficient (rho)) measures the correlation of observations within a group/cluster. It indicates the dependency of observations on the group/cluster they belong to. Mathematically, it is calculated as the variance between groups/clusters divided by the total variance (which is variance between groups plus variance within groups). Thus, the higher the correlation within the groups (meaning less variability within groups/clusters), the lower the variance within groups leading to a higher ICC. The converse is also true, in that the lower the correlation within groups (meaning less variability within groups/clusters), the higher the variance within groups leading to a lower ICC.

Table 2: Power and sample size (total number of symptomatic contacts of index TB patients) estimation

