The effect of the intervention will be assessed for implementation effectiveness, clinical effectiveness, public health effectiveness, and timeliness. Other analyses include equity, as determined by stratified analyses specific to sub-groups of interest. The primary trial analysis is implementation effectiveness; other analyses are secondary. The intervention effect will be measured as the ratio of outcomes in the intervention period (numerator) to those in the pre-intervention/control period (denominator), adjusting for potential confounders and clustering. The data in this trial are hierarchical and clustered. As a practical matter, data are clustered at 2 levels; first, the household (index patient) cluster, including any contacts of index patients and likely from multiple households around the index patient; and second, at the clinic level - multiple CHWs are working towards care. The clinic-level variance will be adjusted for as a random effect. It might lead to similar levels of completion. Analyses will adjust for clustering at those levels with outcomes will be aggregated at the clinic level to give more stable proportions. As indicated in sections 2.9 to 2.11, *iib*, proportion outcomes will be assessed as the difference in log odds of the outcome between the intervention and control exposure periods using the mixed-effects logit model. When the proportion with the outcome is $>15\%$, odds ratios yield biased estimates; in these cases, we will determine the intervention effect by comparing prevalence risk ratios (PRRs) / proportion ratios (PRs) rather than ORs. To achieve this, we will use a modified mixed-effects Poisson generalized linear model (Stata command: meglm) with family(poisson) link(log), which estimates prevalence risk ratios (PRRs)/proportion ratios (PRs) and mitigates the overestimation effect of ORs when the proportion with the outcome is greater than 15%. These models will be used for the proportion of outcomes (implementation effectiveness and clinical effectiveness). Mixed effects Poisson models (mepoisson) will be used for count outcomes (public health effectiveness). For time-to-event outcomes, mixed effects parametric survival analysis models (mestreg) will be used.

The random intercept and random slope models take the general form of

$$Y_{ijk} = \mu + \beta_j + \theta X_{ij} + u_i + e_{ijk}, \dots \quad \text{Equation 1}$$

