where y_{ijk} is the outcome of individual k in period j from clinic i , μ is the mean outcome in the first period, β_j is the difference between period j and the first period with $\beta_1=0$, θ is the intervention effect, X_{ij} is 1 if cluster i received the intervention in period j and 0 otherwise, u_i is a random effect for cluster, and e_{ijk} is the within-cluster variability.

In a stepped wedge trial, the outcomes will be aggregated at cluster level hence the general model form will be

$$Y_t = \mu + \beta_j + \theta X_{ij} + u_i + e_{ijk}, \dots \quad \text{Equation 2}$$

where Y_t = aggregated outcome within each time slice t , calculated from Y_{ijk} (for i exposure, j period (month) and cluster k). We will adjust for unbalanced time-independent variables at baseline and confounders. The proportion of the outcome variable will be calculated for each site and cluster for each study time-exposure slice.

For between-period (horizontal) comparisons, comparative analysis is done at cluster level hence the general model form is:

$$\text{logit}(Y_{jt}) = \alpha + \beta x_{jt} + \sum \gamma_t z_t + u_j \dots \quad \text{Equation 3}$$

where j indexes the clusters, t indexes the steps, x_{jt} indicates a cluster and exposure; is coded 0 when the j th cluster is in pre-intervention (control) exposure and 1 when it is in the post-intervention (intervention); β represents the intervention effect, γ_t represents the time-specific effects, z_t the steps and u_j represents the cluster-level random effects (within-cluster correlation).

Within-period (vertical) comparisons are done by fitting a model as in Equation 4

$$\text{logit}(Y_{jt}) = \alpha + \beta x_{jt} + \sum \gamma_t z_t + u_j \dots \quad \text{Equation 4}$$

- where x_{jt} indicates a cluster and time and is coded 0 for clusters in pre-intervention (control) exposure and 1 for clusters in the post-intervention (intervention); β represents the intervention effect, and γ_t represents the time vertical slices.

Alternative Statistical analyses[§]

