Version 2.0 Update: It was noted above that on 15 October 2022, the President of Uganda announced Ebola-related public health restrictions preventing public movement in two districts where two study sites are located: Mubende and Kasambya. As a result, the principal investigators immediately paused all new introductions of the study intervention according to the schedule noted above. The effects and the duration of this public health emergency are currently unknown, but they may adversely affect both the implementation of this trial and its outcomes. The alternate analysis plans below may become especially relevant if this outbreak invalidates previous assumptions about participant and/or outcome accrual and feasible analytical approaches.

We face a high-level of uncertainty about how the Ebola outbreak and/or other secular trends will affect participant and/or outcome accrual or prior assumptions about sample size and feasible analytical approaches. Accordingly, we lay out our proposed approach below, based on currently available information and our desire to pre-specify the analysis, while recognizing that there may be need to alter these plans if we encounter problems with the analysis, with appropriate justification. The flexibility of our analysis options highlights a strength of the trial design: that is, its pragmatism in the face of an extreme event.

Individual level data will be collapsed at health facility and cluster levels by trial month in both control and intervention exposure periods to create panel data. We will estimate the difference in primary outcome by comparing control and intervention periods using aggregated data. Two models will be considered namely 1) **Random effects logit model (xtlogit)** for binary dependent outcome where the probability of the outcome is determined by the cumulative logit distribution function and accommodates various correlation structures; and 2) **Random effects GEE model (xtreg, re)**; this model accommodates fewer correlation structures than

the former. Both models allow cluster-level aggregated data to vary across time by cluster. The multivariable model will include cluster-level covariates. We will test various correlation structures and choose the final model using likelihood ratio tests and information criteria (AIC, BIC and QIC).

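### The SAP's effect equations carry only a time-constant clinic random intercept, so the logit and Poisson tests can be too liberal if clinics drift over time; by how much depends on an unstated cluster autocorrelation and on the model used.

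*SAP*

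**What the plan says.** Section c (Intervention Effect Analysis) of the SAP's Statistical Methods states: "The clinic-level variance will be adjusted for as a random effect". Equations 1–4 then contain period effects shared by all clinics, one intervention effect and one cluster random effect. In Equations 1 and 2 the remainder is within-cluster variability. No equation has a term for a clinic in a particular period.

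The prose is wider than the equations. Statistical Methods calls the models cluster-period mixed-effects models without defining the phrase. Equation 1 is introduced with "The random intercept and random slope models take the general form of", but no slope follows. Section c also mentions clustering by index patient, and replaces the logit by a log-link Poisson model when a proportion exceeds 15%, without naming a variance estimator. Alternative Statistical analyses proposes to choose among correlation structures by likelihood ratio tests and information criteria, for a fallback analysis of aggregated data.

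The power section works from "assuming a rho-alpha of 0.172 and rho-beta of 0.647 from our preliminary data" and "Test statistic: Wald Z-Test". The protocol's Sample Size section works from a different value: "assuming a clinic intra-cluster correlation coefficient (ICC) of 0.043". Neither document gives a CAC, a between-period ICC or a small-sample correction for 12 clinics.

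**The concern.** In a stepped wedge the effect is estimated largely from change within clinics over time. A time-constant intercept makes two contacts seen a year apart in one clinic as alike as two seen in the same block. If a clinic's completion rate moves for its own reasons, such as staff turnover, supply or local leadership, common period effects cannot absorb the movement. A logit or Poisson model without a clinic-by-period term then counts it as sampling error. The standard error is too small, the interval too narrow and the type I error too high.

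The documents expect such movement. The SAP plans for dropping a whole pair of sites when secular events depress accrual, and the protocol allowed for 20% site dropout before the trial from changing circumstances or leadership.

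**Working it through.** **1. The SAP's own power figure.** Inputs from the SAP power section: K = 12 clinics, T = 7 periods, 11 contacts per clinic-period, ICCs 0.172 and 0.647, 0.4 to 0.6. N = 1 × 11 × 7 × 12 = 924, as stated. With v = p1(1 − p1) = 0.24, take clinic variance τ² = 0.24 × 0.172 = 0.0413 and clinic-period residual σ² = 0.24 × (1 − 0.647)/11 = 0.0077. The random-intercept stepped-wedge variance is

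Var = Kσ²(σ² + Tτ²) / [(KU − W)σ² + (U² + KTU − TW − KV)τ²]

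Here U (treated cells) = 42, W (squared period totals, summed) = 364 and V (squared clinic totals, summed) = 182, so the brackets are 140 and 560. SE = 0.0337, z = 0.2/0.0337 = 5.94, power above 0.999. The four-step row of Table 2 (0.2 to 0.4) gives SE 0.0409, z = 4.89 and power 0.9983, equal to the printed value. So the planned precision also rests on a clinic intercept alone.

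**2. Rough size of the problem.** CAC is an assumption here. A fraction (1 − CAC) of the clinic variance is specific to the period. If the effect were estimated wholly within clinics and the variances were known, true SE / model SE = √{[0.172(1 − CAC) + r]/r}, with r = (1 − 0.172)/11 = 0.0753.
- CAC 0.8: √(0.1097/0.0753) = 1.21, so 2[1 − Φ(1.96/1.21)] ≈ 10%.
- CAC 0.5: √(0.1613/0.0753) = 1.46, so about 18%.

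This is only a rough guide, so the models were simulated.

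**3. Simulation under the null.** 12 clinics, 8 blocks, each clinic's transition block removed; clinic variance on the logit scale ICC/(1 − ICC) × π²/3, split by CAC; two-sided z test at 5%; 3,000 trials per row (500 for the last column). Monte Carlo error is about 0.4 points (1 point for the last column). Rejection rates in %:

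| Baseline, ICC, CAC, contacts per block | Logit, clinic intercept | Poisson, model SE | Linear, clinic-period proportions | Logit + clinic-by-period |
|---|---|---|---|---|
| 20%, 0.172, 1.0, 11 | 4.8 | 2.9 | 5.5 | 6.2 |
| 20%, 0.172, 0.9, 11 | 6.9 | 3.5 | 6.1 | 6.8 |
| 20%, 0.172, 0.8, 11 | 8.0 | 4.4 | 6.2 | 6.6 |
| 20%, 0.172, 0.5, 11 | 11.5 | 7.2 | 5.8 | 6.4 |
| 40%, 0.172, 0.8, 11 | 9.3 | 3.2 | 6.2 | 7.4 |
| 40%, 0.172, 0.5, 11 | 13.1 | 5.6 | 6.0 | 7.0 |
| 20%, 0.172, 0.8, 23 | 11.8 | 6.8 | 6.6 | 8.6 |
| 40%, 0.172, 0.8, 44 | 19.1 | 7.7 | 5.6 | 7.4 |
| 20%, 0.172, decaying 0.8, 11 | 14.4 | 9.7 | 8.8 | 10.4 |
| 20%, 0.043, 0.8, 11 | 5.3 | 3.7 | 5.1 | 3.6 |

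A separate run at a 30% baseline and ICC 0.172 gave, at CAC 0.8 and 0.5, logit 8% and 11% and Poisson 3.5% and 6% with 11 contacts. With 22 contacts the logit gave 13–21% and the Poisson 7–10%.

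Blocks of that size are plausible. The SAP reports 273 index patients in 12 clinics over the two pre-trial months (273/12 = 22.75) against the 11 assumed, and the protocol considers 23 contacts per block.

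**4. Variance estimator.** The Poisson model with clinic-robust standard errors and a z test rejects in 10–11% of trials in nearly every scenario, including CAC 1.0. That excess comes from having 12 clinics. A t reference on 10 degrees of freedom brings it to 6–8%.

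**5. A low-proportion secondary outcome.** Assuming a 4% yield, an ICC of 0.1 and 60 contacts per block (pre-trial: 781/12 = 65 contacts), logit and Poisson both reject 8–10%.

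**The case against.** Four points weigh against the concern.

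- **The primary model is probably Poisson.** Every assumed primary proportion lies between 20% and 60%, so the SAP's 15% rule applies. Poisson variance is too large for binary data and offsets the missing term: about 3–7% at planned size with exchangeable shocks. This stands, but the offset is accidental and shrinks with larger blocks, decaying correlation or rare outcomes. The SAP also names the logit for the primary outcome.
- **Aggregation.** In a linear model on clinic-period proportions the residual absorbs exchangeable shocks, and the test is near nominal. This stands for Equation 2 fitted that way, but not for the logit or Poisson models.
- **The wording may intend more.** Cluster-period, random slope and the choice of correlation structures could signal time-varying clinic effects. But the first is undefined, the second is missing from its own equation, and the third belongs to the fallback analysis and is data-driven.
- **ICC.** With the protocol's 0.043 and 7–11 contacts, inflation is negligible. This stands.

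A reader might also infer that the Ebola restrictions, "preventing public movement in two districts where two study sites are located: Mubende and Kasambya", drive the problem. The documents do not support that. The legend to SAP Figure 2 describes that window as an enrolment pause, although Trial Design says only that new introductions were paused. In simulation (40% baseline, CAC 1, logit model), a one-period drop in two clinics of 1 on the logit scale gave 5.2% and a drop of 2 gave 7.2%, against 6.2% with no shock. The Poisson model stayed near 2%.

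**Conclusion.** The concern holds in conditional form. The equations omit a clinic-by-period effect, disagree with the prose around them and assume a CAC of 1. At ICC 0.172, logit type I error is about 7–9% (CAC 0.8–0.9) or 11–13% (CAC 0.5) with 11 contacts per block, and about 13–21% at 22. Poisson with model-based standard errors gives about 3–7% and 7–10%.

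A reader might conclude that the primary test rejects a true null two to three times too often. That cannot be stated as fact. It needs the logit model, the higher ICC and a CAC of roughly 0.5–0.7 at planned size, or larger blocks or decaying correlation. No CAC is given, and the SAP's 15% rule points to Poisson. Severity: should-fix.

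**What to change.** Add a clinic-by-period random intercept to the logit and Poisson mixed models for the primary and secondary proportion and count outcomes, and keep it whatever its estimated size. Rewrite Equations 1–4 and the cluster-period and random-slope wording to match. Report within-period and between-period ICCs. Name the variance estimator and a small-sample correction for 12 clinics, for example a t reference. The added term with a plain z test still gave about 6–9% for exchangeable shocks and 10–11% for decaying correlation, so the term alone is not a full cure.

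The cost is SAP wording, one variance component and wider intervals where clinic-by-period variation exists. Putting σ² = 0.24 × [0.172(1 − CAC) + 0.353/11] and τ² = 0.24 × 0.172 × CAC into the formula above, the SE for 0.4 to 0.6 at N = 924 rises from 0.034 to 0.048 (CAC 0.8) or 0.062 (CAC 0.5). Power falls from above 0.999 to 0.987 or 0.902. That uses the SAP's residual, which removes the index-patient variance although it assumes one contact per index patient. With (1 − 0.172)/11 instead, power is 0.975, 0.910 and 0.807 at CAC 1, 0.8 and 0.5.

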- a) *Outcome definition:* Number of contacts who complete TB evaluation within 60 days (ctevalcomplete60) of index patient treatment initiation divided by the total number of contacts screening TB symptom positive (ctevaleligible). This will be an aggregate, cluster-level, exposure-specific (control versus intervention) measurement.
- b) *Outcome analysis:* Difference in log odds of the outcome between the intervention and control exposure periods using the Logit model (*n.b.*, this will be the same for all proportional outcomes)

Secondary Outcomes

- a. **Effectiveness** (*i.e.*, clinical effectiveness)
 - i. Proportion of contacts diagnosed with active TB (also known as the active TB treatment yield of TB contact investigation, or the number needed to screen):
 - a) *Outcome definition:* Number of contacts diagnosed with active TB (definitions below) and initiated on treatment within 60 days of index patient treatment initiation divided by the total number of contacts encountered.
 - (i) Microbiologically confirmed active TB: Diagnosed by a positive AFB-smear microscopy result, GeneXpert result, or other accepted *Mtb*-specific microbiologic test (*e.g.*, urinary LAM or mycobacterial culture)
 - (ii) Clinically confirmed active TB: Active TB diagnosed clinically, based on clinically diagnosed extra-pulmonary TB or a decision to initiate presumptively for active pulmonary TB.
 - b) *Outcome analysis:* As above
 - ii. Proportion of contacts initiating TB preventative therapy (TB preventative therapy yield of TB contact investigation):
 - a) *Outcome definition:* Number of TB contacts initiated on TB preventive therapy within 60 days of index patient treatment initiation divided by the total number of contacts eligible for TB preventive therapy
 - (i) Children under age 5
 - (ii) Persons living with HIV
 - (iii) Older adolescent (age ≥ 15 years and adult household and other close contacts with a positive TST and in whom active TB has been excluded by symptoms and/or testing)
 - b) *Outcome analysis:* As above
- b. **Public Health Impact** (*i.e.*, public health effectiveness)
 - i. Count of contacts diagnosed with active TB:
 - a) *Outcome definition:* Number of contacts diagnosed with active TB (definitions below) and initiated on treatment within 60 days of index patient treatment initiation
 - (i) Microbiologically confirmed, as defined above
 - (ii) Clinically confirmed, as defined above

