This sequence of allocation restricted by sites will be determined through a two-stage random drawing during a public randomization ceremony held in Kampala, Uganda. A senior clinician representative of each health center (e.g., the TB focal person), the Health Facility Administrator-in-Charge, and the District Health Officer will be invited to attend a public randomization ceremony chaired by the Uganda NTLP Director. In the first, so-called “Cluster Stage”, health facilities will be divided into high-volume and low-volume strata for cluster assignments. Each health center representative will draw, without replacement, one ball labeled with the cluster designation, until all sites are assigned in paired clusters. In the second and final, or “Group Stage,” the two representatives of each cluster will assign one representative to draw, without replacement, 1 of 6 balls (labeled 1, 2, 3, 4, 5, 6) from an opaque bag to choose the group. Group 1 will be the first group to cross over, Group 2 the second to cross over, and so on. The sites will follow this cross-over sequence at equally spaced, 2-month intervals during the trial period, starting at the beginning of month 3.

Statistical Methods

For standardization purposes, the start of effective intervention exposure for clusters will be considered the first Monday of the next calendar week after the end of each 8-week transition period. This standardization will help fix the trial period slices and improve statistical efficiency for the within-period analyses. We will use a cluster-period mixed-effects logit model[5, 6] to assess differences between post-intervention and pre-intervention periods with regard to the proportion of contacts who completed TB evaluation within 60 days of index treatment initiation, the proportion of contacts diagnosed with active TB, the proportion of contacts initiating TB preventative therapy and proportion of all TB cases among contacts. We will use a cluster-period mixed-effects Poisson model[5, 6] to assess the difference between post-intervention and pre-intervention periods with regard to the count of contacts diagnosed with active TB and the count of contacts initiated on TB preventative therapy within and between periods. We will test for secular trends using both fixed and random effects. If secular trends are present, we will use a segmented regression model.

a. Dataset assembly, cleaning, and creation of new variables

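### For the primary outcome the SAP's 15% rule replaces the stated logit with a Poisson ratio model that has no stated variance or small-sample reference, and the promised index-patient level is in no equation

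*SAP*

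**What the plan says.** - **SAP, Outcomes, Primary Outcome.** The outcome is described thus: "This will be an aggregate, cluster-level, exposure-specific (control versus intervention) measurement". The analysis is: "Difference in log odds of the outcome between the intervention and control exposure periods using the Logit model", and the same is to apply to all proportions.
- **SAP, Statistical Methods.** "We will use a cluster-period mixed-effects logit model[5, 6] to assess differences between post-intervention and pre-intervention periods". Then: "If secular trends are present, we will use a segmented regression model".
- **SAP, c. Intervention Effect Analysis.** The logit is restated. For proportions above 15% the section then says that "odds ratios yield biased estimates; in these cases, we will determine the intervention effect by comparing prevalence risk ratios", and gives the model: "we will use a modified mixed-effects Poisson generalized linear model (Stata command: meglm) with family(poisson) link(log), which estimates prevalence risk ratios". On scope: "These models will be used for the proportion of outcomes (implementation effectiveness and clinical effectiveness"). For counts: "Mixed effects Poisson models (mepoisson) will be used for count outcomes (public health effectiveness"). The section recognises two levels of clustering, index patient and clinic, and says that analyses will adjust for both. It names a random effect for clinic only, and also says that outcomes will be aggregated by clinic.
- **SAP, Equations 1–4.** Each has one cluster effect. Equations 1–2 are linear with a residual; Equations 3–4 are logit without one.
- **SAP 3.1.2, b. Adjusted analyses.** Individual-level analysis if secular trends are present, aggregated analysis by site and month if not.
- **SAP, Power and sample size calculation.** A Wald z-test. No section gives a small-sample correction for 12 clinics.
- **Protocol, item 13, Statistical Considerations.** Multilevel logistic models adjusted for both levels. The SAP takes precedence over the protocol where they differ.

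**The concern.** The primary effect measure and its standard error should follow from one reading of the SAP. Here three places give a log odds difference, and a fourth changes it to a ratio of proportions under a condition that the planning figures always meet. The replacement model is specified by command, family and link, but not by variance. For a yes/no outcome that omission decides the test: the Poisson model gives each observation variance p, where the true value is p(1−p). The usual repair, a robust variance, rests here on only 12 clinics. The index-patient level raises a further question, because a model that treats correlated contacts as independent understates its standard error. At stake is whether a nominal 5% test is a 1% test or a 10% test, and which effect measure is reported.

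**Working it through.** **1. Which model applies.** Planning proportions for the primary outcome: 0.20 to 0.35 and 0.20 to 0.30 (protocol, Sample Size); 0.40 to 0.60 (SAP power text, which calls the outcome treatment completion); 0.20 or 0.25 to 0.40, 0.45 or 0.50 (SAP Table 2). The smallest is 0.20. The SAP does not say whether the control, intervention or pooled proportion is compared with 15%, but all exceed it, so the rule selects Poisson. The effect measure changes:

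| Control, intervention | Odds ratio | Ratio of proportions |
|---|---|---|
| 0.20, 0.40 | (0.4/0.6)/(0.2/0.8) = 2.67 | 2.00 |
| 0.25, 0.45 | 2.45 | 1.80 |
| 0.40, 0.60 | 2.25 | 1.50 |

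**2. The plan's own figures.** N = m·g·T·K = 1·11·7·12 = 924, as stated. Table 2 power follows from the standard stepped-wedge variance

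Var = Kσ²(σ²+Tτ²) / [(KU−W)σ² + (U²+KTU−TW−KV)τ²],

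where U is the number of intervention cells and W and V are the sums of squared period and clinic totals of those cells. For 8 clinics, 0.20 vs 0.40: σ² = (1−0.647)(0.16)/11 = 0.005135; τ² = 0.172·0.16 = 0.02752; T = 5, U = 20, W = 120, V = 60. Var = 0.005863/3.5078 = 0.001671, SE = 0.0409, power = Φ(0.2/0.0409 − 1.96) = 0.9983, as printed. This is a z-test on a difference of proportions. It is the power of neither candidate model.

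**3. Model-based Poisson, by hand.** The within-clinic SE is too large by 1/√(1−p): 1.12 at p = 0.2, 1.29 at 0.4, 1.58 at 0.6. Under the null the effective critical value is 1.96·1.118 = 2.19 at 0.2 and 1.96·1.291 = 2.53 at 0.4, so two-sided rejection is about 2.8% and 1.1%.

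**4. Simulation.** Design: 12 clinics in 6 pairs, 8 periods, each site's transition period dropped (12·8 − 12 = 84 clinic-periods), period fixed effects, no secular trend. ICCs are 0.172 and 0.647 (SAP), on a latent or outcome scale. There are 7, 11 or 23 index patients per clinic-period, with exactly one symptomatic contact each or a Poisson number with mean 1. The ICC scale and the spread of contacts are assumptions. True-null rejection at nominal 5% (300–800 runs per scenario; Monte Carlo SE about 0.8–1.3 points at 5%, up to 1.9 at 10–14%):

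| Analysis | One contact | Contacts vary |
|---|---|---|
| Poisson, model-based, z | 0.8–3.0% | 2.3–5.3% |
| Poisson, clinic sandwich, z | 8.7–11.5% over both | |
| Poisson, clinic sandwich, t on 10 df | 6.0–8.8% over both | |
| Logit, clinic effect only, z | 4.8–6.4% | 8.8–12.3% |
| Logit, clinic and index effects, z | not identified | 4.4–6.6% |
| Same, t on 10 df | not identified | 2.4–3.8% |

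A separate simulation (1,000 runs, 11 contacts per clinic-period, null 0.2 / 0.4) gave model-based Poisson 2.0% / 0.8%, sandwich 9.5% / 9.3% (6.2% / 6.1% with t) and logit 4.6% / 4.4%. With two contacts per index patient the clinic-only logit rejected 10.9%.

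A linear mixed model on clinic-period proportions, with estimated residual and clinic effect only, behaved differently when contacts vary: 5.8–7.3% (z) and 3.3–4.4% (t on 10 df), and 4.8–5.0% in a further run.

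**5. Power, one contact per index patient.**

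| | 11 contacts per clinic-period | 23 |
|---|---|---|
| 0.2 vs 0.4, Poisson model-based / logit | 85% / 93–94% | 99% / 100% |
| 0.4 vs 0.6, Poisson model-based / logit | 65–67% / 90% | 95% / over 99% |

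These compare analyses on the same data; they do not re-estimate the trial's power.

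**6. Do contacts vary within index patients?** The SAP power text takes an average of 1 symptomatic contact per index patient and its Summary a minimum of 1. Together these force exactly one each, in which case the missing index term does no harm. The protocol gives 588/2304 = 0.26, which contradicts the minimum. The SAP's 2.86 contacts per index patient times the protocol's 588/1764 = 1/3 gives 0.95 on average, which leaves the spread open.

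**7. Secular trends.** Statistical Methods answers them with segmented regression; Adjusted analyses answers them with a change from aggregated to individual-level data. Neither mentions the other.

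**The case against.** The strongest reply is that the SAP does decide. The 15% rule is explicit, the logit remains for outcomes at or below 15%, and a 'modified' Poisson model, set against plain mepoisson for counts, commonly means a robust variance. All of that is fair. It still leaves the variance unwritten, and a robust variance on 12 clinics without correction has its own error.

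The second reply stands in full. A reader might infer that leaving out the index level inflates the error rate in any analysis. The documents do not support this. The primary outcome definition, the dataset section and Equation 2 can be read as an analysis of cluster-period proportions, where within-index correlation enters the estimated residual. The inflation belongs to the clinic-only binomial logit of Equations 3–4, and only if contacts vary.

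A reader might also infer a heavy loss of power throughout. That is not supported either. The loss is large only at 0.4 vs 0.6, which is in neither Table 2 nor the Summary, with 11 contacts per clinic-period, a figure based on what the SAP calls a conservative count of index patients (22.7 per clinic were observed before the trial). The protocol's 7 and 23 are contacts per clinic and block, not index patients (2304/12/8 = 24 of those). They belong to a planning set with other ICCs and effects and should not be joined to the SAP's 0.4 vs 0.6.

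Finally, the section on alternative analyses, with its choice by information criteria, is a fallback tied to the Ebola outbreak and not a rival primary rule. Segmented regression could also be fitted to individual data, so the two secular-trend instructions are unreconciled rather than incompatible.

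**Conclusion.** Wrong as written. The textual conflict is certain and needs no simulation: an unconditional logit in three places, a Poisson ratio model that displaces it at every planning proportion shown, no stated variance or small-sample reference, and a promised index-patient adjustment absent from all four equations. The assumptions that the SAP places in its Supplement Tables S1–S3 could not be checked.

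The error has no single direction. Model-based Poisson is too cautious (about 1–3%) with one contact per index patient. An uncorrected clinic sandwich is too liberal (about 9–11%). The clinic-only logit is sound with one contact and too liberal (about 9–12%) if contacts vary. An analysis of cluster-period proportions stays much closer to its level. These sizes rest on the assumed spread of contacts, the ICC scale and the absence of a secular trend, and are illustrative.

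A smaller point: odds ratios are not 'biased' above 15%. They are a different measure that does not approximate a ratio of proportions.

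**What to change.** Name one primary model, one level of analysis and one variance. Make the primary outcome definition, Statistical Methods, Intervention Effect Analysis, the equations and Adjusted analyses agree, including the action if secular trends are found. Mark the alternative analyses as a fallback and state their trigger. Two workable choices:

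- **(a)** A logit on individual contacts with period fixed effects and random effects for clinic and index patient, in line with the protocol. Report the proportion ratio and risk difference by marginal standardisation. State that the index effect is dropped if nearly all index patients have one symptomatic contact. Pre-state a small-sample reference. With t on 10 df the test is conservative here (2.4–3.8%) and costs power: with contacts varying, 81% to 72% at 0.4 vs 0.6 with 11 index patients per clinic-period, 98% to 95% with 23.
- **(b)** Keep the Poisson ratio model, with a clinic-robust variance and a named bias correction or a randomisation test. t on 10 df alone leaves about 6–9%. The corrected versions were not simulated.

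In either case replace 'biased' by a statement that odds ratios do not approximate a ratio of proportions. The cost is rewording, one random-effect or variance option, and some power for the small-sample reference. No new data are needed.
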